### **1. PURPOSE OF STUDY**

This study represents the second phase of a larger research project developed for a U01 award as part of the Collaborative Initiative on Fetal Alcohol Spectrum Disorders (CIFASD) funded by the National Institute on Alcohol Abuse and Alcoholism (NIAAA). The overall project aims to develop and evaluate a mobile health (mHealth) application (app) for parents/caregivers of children with fetal alcohol spectrum disorders (FASD).

The first phase of this project was approved under IRB protocol #1266 (legacy RSRB#67394). In that phase we used qualitative research methods to engage parents and caregivers in the development of the mHealth intervention and obtain iterative feedback on acceptability and feasibility. A prototype of the app was completed in both iOS and Android and beta-testing was completed with parents/caregivers and providers.

In this second phase of the study, we are aiming to conduct a larger feasibility trial of the app with 60 parents/caregivers. Data collection will include quantitative pre-post surveys and qualitative interviews with a subsample of users. Our hypothesis is that quantitative measures will show improvements in child behavior, parent FASD knowledge, parenting self-efficacy, behavior attributions, family needs met, and parent use of self-care. We also hypothesize parents/caregivers to rate app quality positively. These quantitative indicators are expected to correlate with patterns of app usage. This quantitative data will allow us to calculate pre-post effect sizes, which will inform needed sample sizes for the large-scale hybrid effectiveness-implementation randomized controlled trial (RCT) planned in phase 3 (IRB approval will be obtained prior to phase 3 implementation). Qualitative interview data will provide a rich context for the feasibility of the app and offer further insights into fine-tuning of the app and measurement battery prior to the RCT.

### **2. BACKGROUND AND RATIONALE**

Children with fetal alcohol spectrum disorders (FASD) have significant neurobehavioral impairments that contribute to poor adaptive function and increased behavior problems in home, school, and community settings [1]. Most interventions for preschool and school-aged children with FASD, the largest age group with identified FASD [2], are directed at caregivers or have included parent training to facilitate child skill acquisition [3]. Interventions directed toward caregivers are an essential component of FASD integrated care models [3,4]. Tailored FASD-informed caregiver interventions provide families with the knowledge and skills to better understand their children's development and behavior, generate effective environmental accommodations and behavior plans, teach and generalize targeted child skills, and advocate for their children in school and community settings [3]. These strategies are vital for sustained child improvement and better family adaptation.

Unfortunately, we and others have documented that the vast majority of families cannot access FASD-informed interventions. Barriers to care occur because a knowledgeable and skilled workforce is lacking [5,6], and there are family-level barriers such as limited financial resources, inability to access childcare, and stigma [7]. Access to appropriate FASD-informed care is even more limited in less densely populated areas. Many families try peer-to-peer and self-help strategies, but it can be

difficult to evaluate the credibility and effectiveness of information provided through these modalities.

The primary objective of this project is to develop and evaluate an mHealth app to directly provide caregivers with evidence-based content and peer-moderated support they can easily access and use to improve outcomes for their children and families. The app, called “FMF Connect,” will be derived from our work on the scientifically-validated Families Moving Forward (FMF) Program that has shown promising results for child and caregiver outcomes in three trials with families raising children with FASD [8]-[10].

This project will follow a systematic approach to the development and evaluation of the FMF Connect mHealth intervention. The app will be designed for use by caregivers, will utilize a cloud-based infrastructure, and will build on our existing open source framework for the development of medical apps [11], and those of others [12,13]. Preliminary feasibility tests and iterative feedback from diverse caregivers will aid in fine tuning caregiver instructions, content, and user-interface features throughout the development process. Core content will be provided to all users, with optional features tailored via needs assessment.

In this and subsequent phases, the FMF Connect mHealth intervention will be evaluated to identify the patterns of app usage that relate to the greatest improvements in child and caregiver outcomes. Consistent with prior FMF trials, targeted outcomes include satisfaction, child behavior problems, caregiver FASD/advocacy knowledge, attributions of misbehavior, parenting practices, parenting efficacy, self-care, and social support. This novel mHealth intervention has the potential to reach many families in need and reduce significant barriers to care, resulting in broader public health impact. Project findings will guide further app development both in terms of content and technological advances to optimize intervention effects.

### **3. ADMINISTRATIVE ORGANIZATION**

This study will be conducted through the University of Rochester (UR) and will involve faculty, students, and staff within the following departments and centers: Department of Psychology, Mt. Hope Family Center (MHFC; which is a part of the Psychology Department), Department of Electrical and Computer Engineering (ECE). [name] primary appointment is at MHFC and the Psychology Department. She oversees the study coordinator, research assistant, and graduate and undergraduate students working on the project within these departments. [name] is faculty within ECE and oversees staff and students within these departments contributing to the project. Weekly project lab meetings ensure coordination across all aspects of the project.

All data collection and communication with participants is completed by UR project staff. Consenting and screening data, contact information, and quantitative survey pre-post data will be collected and stored online using REDCap hosted by UR. Participant interaction with the app is recorded using Amazon Web Services (AWS; HIPAA-Compliant). Qualitative interview data will be gathered by research staff using HIPAA-compliant Zoom videoconference application. All paper and electronic files will be securely stored on MHFC servers and in locked cabinets only accessible to UR project staff.

As part of CIFASD, this study may involve data sharing as outlined by the policies and procedures established by CIFASD and required by NIAAA: <https://cifasd.org/data-sharing/>. De-identified data will also be stored in the CIFASD Central Repository hosted at Indiana University (IU), as is required by NIAAA for all projects involved in CIFASD.

### **4. STUDY DESIGN**

This study involves a single arm feasibility trial. Quantitative survey data will be collected prior to intervention delivery and 3-months later. App usage will also be recorded during the 3-month period. After 3 months, a subsample of participants will be selected to complete a qualitative interview about their experiences using the app. Primary study outcomes include child behavior, parent FASD knowledge, parenting self-efficacy, behavior attributions, family needs met, and parent use of self-care. We are also interested in participant perceptions of app quality and patterns of app usage.

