## 5. SUBJECT POPULATION

The subject population will include parents and caregivers of children (ages 3-12) with fetal alcohol spectrum disorders (FASD) or affected by prenatal alcohol exposure (PAE) who live in the United States.

We are aiming to include 60 parents or caregivers with usable data in this study. We expect a portion of families will enroll in the study, but not complete assessments or install the app. In our initial beta-testing trials, 80% of families installed and used the app at least once. Unfortunately, given the COVID-19 pandemic, participation rates are trending lower than observed in prior trials. As a result, we will target 120 parents and caregivers in the trial.

It is also possible that interest in the study will exceed our intended final sample size. Given that informed consent procedures will occur online, we have set the number of subjects at 300. If enrollment quickly exceeds 120, we will utilize stratified random sampling with oversampling of a couple of underrepresented groups (i.e., biological parents, men).

- Strata may include region of the US, operating system (iOS vs. Android), or other variables depending on the number of participants and their relevant characteristics.
- We will plan to oversample any biological parents who enroll in the study (up to 20% of the sample, and then randomize any remaining with the rest of the sample after that), as their perspective is underrepresented in FASD research and they represent an important demographic for FMF Connect.
- We also plan to oversample male participants (up to 20%, and then randomize any remaining with the rest of the sample after that).

Families will be told in the consent document that they will be informed about future trials if they are not selected for the feasibility trial.

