## 9. STUDY PROCEDURES

### Data Collection Procedures

Parents/caregivers who are selected for the study will be sent an email inviting them to complete the baseline study surveys (see survey battery below) administered by REDCap. Any families not selected (either due to ineligibility or not enough available slots) will be informed of their status. Eligible families not selected will also be told that they will be notified when any subsequent intervention trials of FMF Connect are initiated. They can consider at that time if they might like to participate.

Once the baseline surveys are completed, parents/caregivers will receive instructions via email of how to install the FMF Connect app on their phones (see instruction documents and accompanying emails). After three months, parents/caregivers will receive an email with a link to the follow-up surveys (see survey battery below). The assessment battery is estimated to take 35-45 minutes to complete at each timepoint.

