**Table 1. Quantitative Study Battery**

Measure	Baseline	Follow-up
Eyberg Child Behavior Inventory (5-8min)	X	X
Parenting Sense of Competence Scale (3-5min)	X	X
Family Needs Questionnaire (3-5min)	X	X
Knowledge & Advocacy Questionnaire (15-20min)	X	X
Self-Care and Support Assessment (3-5min)	X	X
Adverse Childhood Experiences (2 min)	X	
Family Background & Services Survey (5-10min)	X	X
COVID-19 Experiences Survey (5 min)		X
User Version of the Mobile Health Application Rating Scale (5-8min)		X

Given lower response rates, participants who do not complete the follow-up surveys after receiving the automatic reminders in REDCap will be asked if they are willing to just complete the COVID-19 Experiences Survey. This will provide important data to help us understand how much COVID-19 impacted app usage and study engagement. This will also inform the future RCT design and measurement.

A subsample of participants (up to 30 parents/caregivers) will be invited to complete an individual interview or focus group after completion of the 3-month follow-up assessment. These participants will be selected based on diverse patterns of app usage and other participant characteristics.

The questioning route for interviews/focus groups will cover the following topics: 1) overall

impressions of the FMF Connect app; 2) experience using the app (both facilitators and barriers of use); 3) satisfaction and feedback on individual components of FMF Connect; and 4) perceived impact on self and family. Interviews/focus groups are expected to take about 60-90 minutes each. Audio recordings of interviews/focus groups will be transcribed for later analysis.

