## 19. DATA ANALYSIS PLAN

### **Aim 1: Pilot the Pre-Post Assessment Battery and Estimate Intervention Effect Sizes**

Descriptive statistics and reliability indices will be calculated for all measures at each time point. Analysis of Variance (ANOVA) techniques and effect size calculations will be used to estimate the magnitude of intervention effects. These analyses will inform power analyses for the future large-scale RCT and refinement of the measurement battery.

Additional correlational and regression analyses will also be undertaken to get a preliminary sense of how outcomes relate to patterns of app usage.

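### Does the primary outcome of behavior attributions lack a measure, since no title in Table 1 and no line of the analysis plan names one?

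*Combined protocol and SAP*

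**What the plan says.** Section 4 (Study Design) sets out the outcomes: "Primary study outcomes include child behavior, parent FASD knowledge, parenting self-efficacy, behavior attributions, family needs met, and parent use of self-care". Section 1 (Purpose of Study) makes the same six the subject of the pre-post hypothesis, expecting that "quantitative measures will show improvements in child behavior, parent FASD knowledge, parenting self-efficacy, behavior attributions, family needs met, and parent use of self-care". Section 2 also lists attributions of misbehavior among the targeted outcomes, apart from knowledge and parenting efficacy, so the investigators treat it as a construct of its own.

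Table 1 in Section 9 is the survey battery. It gives nine questionnaires by title, expected minutes and time point; six are given at both baseline and follow-up. It does not say which outcome each one measures, and it lists no subscales.

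The quantitative analysis plan (Section 19, Aim 1) is equally general: "Descriptive statistics and reliability indices will be calculated for all measures at each time point". It then refers to ANOVA techniques and effect sizes without naming a score.

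**The concern.** A reader who checks the six outcomes against Table 1 finds a likely home for five and none for the sixth. Two harms could follow.

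- **The construct is not measured.** The trial would then give no effect size, standard deviation or reliability for it, although supplying these for the phase 3 trial is the purpose of Aim 1. The loss could not be repaired for people already enrolled, because app installation follows the baseline surveys and a pre-app score cannot be collected afterwards.
- **The construct is measured inside another questionnaire.** The score that counts as the attribution outcome would then be unspecified and could be chosen after the data are seen. An effect size picked that way would carry a favorable bias into the planning of phase 3.

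**Working it through.** The documents give no figure for this point to reproduce, so the check is a comparison of texts, followed by a sum for the cost of one remedy.

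**Step 1. Match outcomes (Section 4) to Table 1 rows given at both time points.**

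| Primary outcome | Row suggested by title |
|---|---|
| Child behavior | Eyberg Child Behavior Inventory |
| FASD knowledge | Knowledge & Advocacy Questionnaire |
| Parenting self-efficacy | Parenting Sense of Competence Scale |
| Family needs met | Family Needs Questionnaire |
| Self-care | Self-Care and Support Assessment |
| Behavior attributions | none |

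The sixth pre-post row is the Family Background & Services Survey. The other three rows (adverse childhood experiences, COVID-19 experiences, app rating) are each given once. Result: 5 of 6 outcomes matched; 0 of 9 rows name attributions.

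**Step 2. Ask what the match proves.** All five pairings are inferences from titles, since the protocol assigns no outcome to an instrument. Titles are also an incomplete guide. Section 2 lists self-care and social support as two targets, yet one row of Table 1 appears to serve both. The Knowledge & Advocacy Questionnaire is the longest in the battery at 15-20 minutes; that it yields more than one score is possible but not shown. The comparison therefore supports *not identified*. It does not support *not measured*.

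**Step 3. Read the analysis plan.** Section 19 names no instrument, subscale or score for any of the six outcomes. On scoring, attributions stand where the other five stand. What is particular to attributions is that the instrument cannot be guessed from a title.

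**Step 4. Cost of adding a scale.** Inputs are the minutes in Table 1, in row order for each time point.

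- Baseline, low: 5+3+3+15+3+2+5 = 36. High: 8+5+5+20+5+2+10 = 55.
- Follow-up, low: 5+3+3+15+3+5+5+5 = 44. High: 8+5+5+20+5+10+5+8 = 66.
- Stated in Section 9: "The assessment battery is estimated to take 35-45 minutes to complete at each timepoint".
- With one more scale of 3-5 minutes (an assumption, equal to the shortest outcome questionnaires listed): 39-60 at baseline and 47-71 at follow-up.

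The listed maximum already exceeds the stated 45 minutes by 10 at baseline (55 - 45) and by 21 at follow-up (66 - 45). Section 5 reports that "participation rates are trending lower than observed in prior trials", and the text under Table 1 opens a reduced follow-up with "Given lower response rates, participants who do not complete the follow-up surveys". Both remarks suggest that collection may have begun, in which case a new scale could not supply baselines for those already using the app.

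**Step 5. Weigh each possible change.**

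- *Name an existing subscale.* This records what the investigators must know in order to score their own battery. It alters neither data collection nor the method of analysis.
- *Add a scale.* This trades one more outcome against burden and response in a trial already short of both time and responders. It is debatable, and its need is unproven.
- *Remove the outcome.* This is wrong if the items are being collected, and it is a change of primary outcome if collection has begun.

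**The case for a change.** The strongest reply is that a primary outcome should be traceable to a score in the document itself, and that a trial whose first aim is to pilot a battery has special reason to say which measure gives which effect size. Attributions are the one outcome a reader cannot trace even by inference. Table 1 is fully legible, so no lost text in it explains the gap. An unnamed score also leaves room for selection after the fact.

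Much of this stands. The omission is real, and a line naming the measure would have helped. Two parts do not carry through. The lost effect size and unrecoverable baseline arise only if no listed questionnaire contains attribution items, which the documents neither confirm nor exclude. The freedom to choose a score applies to all six outcomes, and it matters less here than in a confirmatory trial: the design is single-arm and states no alpha, power target or threshold for success. Selection could still bias a planning figure, so that risk is limited rather than absent.

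**Conclusion.** The observation is accurate but does not call for a change to the plan. One of six primary outcomes has no identifiable instrument, and none of the six has a named score. This is missing detail that the investigators can fill from the questionnaires they hold.

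The conclusion rests on two assumptions: that the investigators know which items, if any, measure attributions, and that they will report the outcome according to what was collected. If nothing in the battery measures it, the report will have no attribution effect size, and results for the other five outcomes stand as planned.

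The gap between the summed and stated survey times is a separate, minor inconsistency. No result of the trial depends on the 35-45 minute estimate.

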## 5. SUBJECT POPULATION

The subject population will include parents and caregivers of children (ages 3-12) with fetal alcohol spectrum disorders (FASD) or affected by prenatal alcohol exposure (PAE) who live in the United States.

We are aiming to include 60 parents or caregivers with usable data in this study. We expect a portion of families will enroll in the study, but not complete assessments or install the app. In our initial beta-testing trials, 80% of families installed and used the app at least once. Unfortunately, given the COVID-19 pandemic, participation rates are trending lower than observed in prior trials. As a result, we will target 120 parents and caregivers in the trial.

It is also possible that interest in the study will exceed our intended final sample size. Given that informed consent procedures will occur online, we have set the number of subjects at 300. If enrollment quickly exceeds 120, we will utilize stratified random sampling with oversampling of a couple of underrepresented groups (i.e., biological parents, men).

- Strata may include region of the US, operating system (iOS vs. Android), or other variables depending on the number of participants and their relevant characteristics.
- We will plan to oversample any biological parents who enroll in the study (up to 20% of the sample, and then randomize any remaining with the rest of the sample after that), as their perspective is underrepresented in FASD research and they represent an important demographic for FMF Connect.
- We also plan to oversample male participants (up to 20%, and then randomize any remaining with the rest of the sample after that).

Families will be told in the consent document that they will be informed about future trials if they are not selected for the feasibility trial.

## 6. INCLUSION AND EXCLUSION CRITERIA

Inclusion criteria:

- Biological parent or other primary caregiver (e.g., foster or adoptive parent, relative, legal guardian) of a child with FASD or PAE
- The parent/caregiver must be at least 18 years old
- The child must be between the ages of 3 and 12 years old (if there is more than one child in the family with FASD/PAE in this age range, the parent/caregiver is instructed during screening to choose one to complete study surveys about)
- The child has a diagnosis of FASD or has confirmed PAE
- The child has lived with the parent/caregiver for at least 4 months and is expected to remain in the home for at least 1 year
- The parent/caregiver lives in the United States
- The parent/caregiver has a smartphone with iOS or Android operating system

Exclusion criteria:

- The parent/caregiver is not fluent in English (the FMF Connect app and pre-post measures are currently only available in English)

- There is another parent/caregiver of the same child or living in the home that is already enrolled in the study (couples are excluded to prevent dependence in the data)
- The family has previously received or is currently receiving the therapist-led Families Moving Forward (FMF) Program

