## 7. RECRUITMENT METHODS

Potential participants will be recruited through a variety of mechanisms, consistent with previous studies in our research group and in CIFASD. The Study Website ([www.fmfconnect.com](http://www.fmfconnect.com)) will include information about the study, as well as a link to the study REDCap Consenting and Screening Module for interested families to enroll.

Information about the study will be disseminated in various ways (see study flyer with link to the Study Website):

- [name] may share study information with eligible families in the RSRB-approved Future Contact Database (RSRB00055352; PI: [name])
- [name] will share study recruitment materials with providers and community advocates who regularly see children with FASD
- CIFASD investigators can inform research participants or patients in their local sites or clinics for which they have routine access
- The National Organization on Fetal Alcohol Syndrome (NOFAS) is a member of CIFASD and has a mission to educate the public about FASD and disseminate research and policy information. They can disseminate the study flyer through their Weekly Round-Up newsletter, significant social media presence, and to their state and local affiliates who can share in their communities
- [name] and other CIFASD investigators may include slides about the study in conference or community presentations
- Organizers/moderators of popular social media groups can be sent the study flyer and can choose to share with their members

As part of CIFASD, we will also try to aid other projects with recruitment from our study sample. Our Consenting and Screening Module includes a question asking if participants are interested in learning about other studies. For those that indicate yes, we will send them any new relevant flyers or information about other consortium projects they might be eligible for. We will submit any flyers and email language in a modification to this study prior to sending to our participants. For example, the DiG Human Genetics Study within CIFASD has previously referred some families to our study. We would like to send their study flyers (see attached flyer and email language) to participants in our sample who indicated they have not previously done the DiG study (in Screening Module).

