Some interested parents/caregivers may have already completed the CIFASD Common Forms through another CIFASD study. To reduce participant burden, participants will be asked prior to completing forms if they have done any of the other current CIFASD studies. If they answer yes, REDCap will be set up to have them skip out on completing the Prenatal Exposure History and FASD Diagnosis History forms. The CIFASD Common Forms for that participant can then be located in the CIFASD Central Repository by their GUID. In the event that a participant answers “yes” to other CIFASD studies, but their data cannot be located (e.g., is not deposited yet, difficulties creating a

GUID due to inconsistent data across studies), we will send participants our forms to complete via REDCap. Logistically, this may require changing their imputed response to “no” to release the forms in REDCap; this change will be documented to file.

After completing the Consenting and Screening module, participants will be notified that project staff will review all submitted information to assess final eligibility. They will also be reminded of the randomization procedures if interest in the study enrollment exceeds targeted sample size.

This study is funded by the National Institute of Health (NIH). A Certificate of Confidentiality is automatically included as part of the notice of award. Language regarding the Certificate of Confidentiality is included in the consent form.

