### **FMF Connect mHealth Intervention**

The FMF Connect intervention includes cloud infrastructure and an innovative, multilayered mobile app. It incorporates tailored content for parents/caregivers of children (ages 3-12) with FASD or PAE. The app integrates five main components: 1) Dashboard; 2) Learning Modules; 3) Family Forum; 4) Library; and 5) Notebook. Weekly emails are also sent to support motivational engagement.

App education, derived from the standard FMF Program, is packaged in easily digestible Learning Modules. The Learning Modules are organized into three levels: 1) Getting Started; 2) Taking Action; and 3) Taking It to the Next Level. Each level is presented incrementally, with content in the subsequent level being made accessible once core content from the prior level has been viewed. The Library provides access to additional optional content that can be downloaded and printed to use in advocacy and skill development. The Notebook is a personalized section that organizes parents'/caregivers' responses to learning activities in a convenient location for later easy access.

The Family Forum serves to 1) engage and facilitate parents'/caregivers' continued utilization of the app, 2) support and extend parents'/caregivers' implementation of new knowledge and skills, and 3) provides peer support, encouragement, and understanding of the parent's/caregiver's own needs. Trained peer moderators will moderate discussion in family forums to ensure safety. They will also provide support and prompt skills or content areas to consider.

The Dashboard displays parent/caregiver progress in Learning Module completion, use of the Family Forum, and daily and weekly ratings imputed by the parent/caregiver. It also includes the Tip of the Day feature.

Complementing the app is a Cloud infrastructure to transparently but securely distribute information, including storing and retrieving data, managing notification and messaging, and synchronizing data on all devices. A local datastore will protect the mobile app against network failures and connectivity issues. This local datastore will be transparently synchronized with the Cloud database so that all the querying and security features will be always available regardless of network connectivity. Updates will be automatically pushed out so users have the latest version.

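### Section 6 does not address caregivers who already had the FMF Connect app in beta-testing, so some baseline surveys could follow exposure to the intervention

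*Combined protocol and SAP*

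**What the plan says.** Section 6 lists three exclusions. One is lack of fluency in English. The second concerns a second caregiver: "There is another parent/caregiver of the same child or living in the home that is already enrolled in the study". The third concerns prior treatment: "The family has previously received or is currently receiving the therapist-led Families Moving Forward (FMF) Program". None names earlier use of the FMF Connect app.

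Such use has occurred. Section 1 reports of phase 1: "A prototype of the app was completed in both iOS and Android and beta-testing was completed with parents/caregivers and providers". Section 5 adds: "In our initial beta-testing trials, 80% of families installed and used the app at least once". The app and the excluded program share content. Section 9, under FMF Connect mHealth Intervention, says: "App education, derived from the standard FMF Program, is packaged in easily digestible Learning Modules".

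Section 4 defines the timing of measurement: "Quantitative survey data will be collected prior to intervention delivery and 3-months later". Sections 1 and 19 say that the resulting effect sizes will feed the power calculations for the phase 3 RCT.

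**The concern.** The plan treats earlier receipt of the therapist-led program as disqualifying. The app's teaching content comes from that program, so earlier use of the app is at least as direct a reason, and the plan gives no rationale for treating the two differently. For a returning beta-tester, the first survey would come after some exposure.

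FASD knowledge, attributions and parenting self-efficacy are things the app aims to change, so a prior user may have less room to improve. Returning users may also be unusually interested in the app, which could affect installation, usage and app-quality ratings. With a single arm and no record of prior use, the results would not reveal either effect.

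**Working it through.** **Does any other part of the plan close the gap?**

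- The second-caregiver exclusion refers to enrolment in this study. Section 1 describes this study as the second phase, so phase 1 participation is not covered.
- Section 8 includes a question on other research: "participants will be asked prior to completing forms if they have done any of the other current CIFASD studies". A yes leads to skipped history forms, not to exclusion.
- Section 7 names a recruitment channel through which the group "may share study information with eligible families in the RSRB-approved Future Contact Database". Whether phase 1 families are in that database is not stated.
- Section 19 plans ANOVA, effect sizes, correlations and regressions. It names no covariate, subgroup or sensitivity analysis for earlier app use.
- Section 8 refers to a Screening Form that is not among the documents.

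The written criteria and the analysis plan therefore leave the gap open.

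**How large could the effect be?** The plan states no expected effect, SD, alpha or power, so it offers no figure of its own to reproduce on this point. The one input taken from it is the 60 caregivers with usable data (Section 5). Everything else is assumed:

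- true effect in app-naive caregivers, d = 0.40 SD
- prior users k = 3, 6 or 12 of the 60, so f = k/60 = 0.05, 0.10 or 0.20
- share of the naive change that prior users still show, r = 0 or 0.5
- RCT with 80% power and two-sided 5% alpha

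Formulas:

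- observed effect = d × (1 − f + r × f)
- n per arm = 2 × (1.960 + 0.842)² / d² = 15.70 / d², rounded up

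Without prior users, 15.70 / 0.16 = 98.1, so 99 per arm.

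| Prior users of 60 | Effect, r = 0 | n per arm | Effect, r = 0.5 | n per arm |
|---|---|---|---|---|
| 3 | 0.40 × 0.95 = 0.38 | 109 | 0.40 × 0.975 = 0.39 | 104 |
| 6 | 0.40 × 0.90 = 0.36 | 122 | 0.40 × 0.95 = 0.38 | 109 |
| 12 | 0.40 × 0.80 = 0.32 | 154 | 0.40 × 0.90 = 0.36 | 122 |

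Using a single-arm pre-post effect as the between-arm effect is for illustration only.

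The formula ignores the small rise in SD when two groups are mixed. With that included, the observed effect is d(1 − f + rf) / √(1 + f(1 − f)(d(1 − r))²), and the pattern is the same. At f = 0.10 and r = 0, d = 0.30 falls to 0.269 (175 to 218 per arm) and d = 0.50 falls to 0.445 (63 to 80 per arm).

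**Comparison with sampling error.** With 60 pairs and d = 0.40, SE = √(1/60 + 0.40²/120) = √0.0180 = 0.134. The shifts in the table run from 0.01 to 0.08, all below one SE. The 95% interval is about 0.40 ± 0.26, or 0.14 to 0.66, which on the same formula spans about 800 to 37 per arm.

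**The case against.** The strongest reply is that nothing shows a single prior user would enrol, and that any plausible dilution is small beside the imprecision of a 60-person feasibility study. Both statements are correct, and they limit the priority of the point. They do not remove it: sampling error is reported in the confidence interval, whereas this bias is not, and it can be avoided at almost no cost.

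A reader might also infer more than the documents support:

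- **That a beta-tester must be accepted.** Staff review final eligibility (Section 8), only selected caregivers are invited (Section 9), and random sampling applies if enrolment quickly passes 120 (Section 5). The text supports only that such a caregiver is eligible as written.
- **That beta-testers are likely to re-enrol.** The recruitment channels make overlap possible. No section says that phase 1 families are in the contact database or would return.
- **That most beta-testers were substantially exposed.** The 80% figure counts a single use of what Section 1 calls a prototype.
- **That the bias must run toward zero.** The plan expects outcomes to correlate with usage, so keen returning users could change more than new ones (r above 1), and the estimate would then rise.
- **That the RCT would be underpowered.** Dilution would enlarge it.
- **That no check exists.** The Screening Form is unseen and may contain one. If it does, Section 6 should say so.

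**Conclusion.** The gap is real but modest. By the written criteria, a caregiver who used FMF Connect in beta-testing qualifies, and that caregiver's first survey would not meet the timing that Section 4 intends. The pre-post effect sizes could be distorted, most plausibly downward though not certainly, and the usage and app-quality results could be affected too.

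The size cannot be derived from the documents. Under the assumed 5% to 20% share of prior users and a 0.40 SD effect, the estimate falls by 0.02 to 0.08 with no further change and by 0.01 to 0.04 with half the change. That is a cheap improvement of optional priority, not a flaw that undermines the study.

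**What to change.** Add one screening item asking whether the caregiver, or another caregiver in the home, has previously had access to the FMF Connect app, phase 1 beta-testing included. Check the answers against the phase 1 participant list. Then take one of two routes:

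1. Add prior access to the app to the Section 6 exclusions.
2. Keep these caregivers but flag them. State in Section 19 that the main Aim 1 effect sizes and the usage rates come from app-naive caregivers, and show results including prior users alongside.

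If enrolment has already begun, the phase 1 list can be used to flag prior users, and the second route still applies.

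The cost is one question and one list check. Exclusion may lose a few volunteers at a time when Section 5 reports falling participation. Flagging avoids that loss but leaves a slightly smaller main analysis set.
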